5.1.5 Protocol deviations

Before database locking, data of all subjects on the CRF will be checked for major protocol deviations. All potential major protocol deviations will be reviewed and evaluated by the investigator and the sponsor.

All major protocol deviations will be summarized and described separately by type and treatment group, and will be tabulated and analyzed.

Definitions of major protocol deviations:

- Serious violation of the inclusion/exclusion criteria;
- Incorrect treatment by study drugs (not treated using the drug or dose as per randomization);
- Other major protocol deviations jointly recognized by the investigator and the sponsor.

5.1.6 Inclusion/exclusion violation

All violations of the inclusion and exclusion criteria will be listed by subject number.

5.2 Study Subjects

The study subjects will be analyzed by treatment group.

5.2.1 Disposition of subjects

The number of screened subjects, number of enrolled subjects, number and percentage of treated subjects, number and percentage of subjects in the analysis sets (including the full analysis set, per-protocol set, safety set, PK concentration set, and immunogenicity analysis set), number of subjects who discontinue study/treatment, and number and percentage of corresponding subjects to the reasons for discontinuation.

5.2.2 Demographics

Age, gender, ethnicity, height, weight, and other demographic data of the subjects will be summarized using descriptive statistics by treatment group.

For continuous variables (such as age, height, weight, body mass index, doxorubicin dose corresponding to cumulative anthracycline, etc.), the number of observed subjects, mean, standard deviation, median, quartile, minimum, and maximum will be listed by treatment group.

For categorical variables (such as gender, ethnicity, ECOG PS, etc.), the frequency and percentage will be listed by treatment group.

Demographic and baseline characteristics will be tabulated.

5.2.3 Tumor diagnosis

The following tumor parameters will be summarized using relevant descriptive statistics: the site of primary lesion, histological type, and clinical stage at screening will be summarized by the number and percentage of subjects involved in each treatment group. The course of disease (year) will be summarized using descriptive statistics such as mean, standard deviation, median, minimum, and maximum. A detailed list of subjects for tumor diagnosis will be provided.

The course of disease (year) is defined as the time from the date of the first diagnosis to the time of randomization, which should be calculated as: (date of randomization – date of first diagnosis + 1)/365.25.

5.2.4 Medical history

A detailed list of subjects and their medical history will be provided.

5.2.5 Tumor treatment history

Tumor treatment history mainly includes the history of tumor surgery, the history of systemic anti-tumor treatment, the history of chemotherapy, and the history of radiotherapy.

For tumor treatment history, the following descriptive statistics will be provided:

- Number and percentage of subjects who have received tumor surgery;
- The number and percentage of subjects who have received chemotherapy;
- The number and percentage of subjects who have received radiotherapy;
- The number and percentage of subjects who have received systemic anti-tumor therapy.

In addition, a detailed list of subjects will be provided.

5.2.6 Prior therapy and concomitant medication

All previous medication, concomitant medication, and concomitant non-drug therapy will be listed.

5.3 Follow-up Systemic Anti-Tumor Therapy

Follow-up systemic anti-tumor treatments will be listed by treatment group.

5.4 Efficacy analysis

5.4.1 Primary efficacy analysis

The primary endpoint of the study is the IRC-assessed PFS (as per RECIST v1.1). The primary analysis will be based on the FAS. The survival functions of PFS of the two groups will be compared using stratified log-rank tests with and without random stratification factors. The Kaplan-Meier method will be used to estimate the PFS rate, plot the survival curve, and estimate the median PFS, and its 95% CI will be calculated (Brookmeyer-Crowley method). The analysis with stratification factors will be used as the primary analysis.

In addition, as a supporting analysis and under the assumption of proportional hazards, the Cox models with and without stratification factors will be used to estimate the hazard ratio (HR) and calculate the corresponding 95% CI (Wald method).

5.4.2 Secondary efficacy analysis

The analysis of secondary efficacy endpoints will be based on the FAS.

For the secondary endpoint PFS assessed by the investigator (as per RECIST v1.1), the analytical method will be the same as that for the primary endpoint mentioned above.

For the objective response rate (ORR) and disease control rate (DCR), the rates in the two groups and their two-sided 95% CI (Clopper-Pearson method) will be estimated, and the inter-group difference of rates and its two-sided 95% CI will be calculated (CMH method). A swimmer plot of ORR will also be produced.

Other endpoints (best overall response, quality of life score, etc.) will be statistically summarized in accordance with general principles.

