[21] Pharmacokinetics/immunogenicity test: Blood sampling time points for pharmacokinetics and immunogenicity study of SHR-1210: within 0.5 h pre-administration on C1D1, C2D1, C4D1, C6D1, C9D1, and every 4 cycles thereafter, with 4-6 mL of peripheral venous blood collected at each time point; 4-6 mL of peripheral venous blood will be collected once at 30 days after the last dose. Blood sampling time points for pharmacokinetics study of apatinib: within 0.5 h pre-administration and 4 h (\pm 10 min) post-administration on C1D1, C2D1, C4D1, and C6D1, with 2-4 mL of peripheral venous blood collected at each time point. The time interval between the administration of apatinib on the day of blood sampling and the previous administration should be no less than 20 h.

[22] Quality of life scoring: Performed within 7 days before the first dose, on day 1 of every 2 cycles from cycle 3 onwards, on day 1 of every 4 cycles from cycle 17 onwards, and at 30 days after the last dose.

- [23] Diary card dispensing, retrieval, and filling: The subjects will measure blood pressure by themselves or others during the treatment period, and shall fill out the diary card every day to record blood pressure and other discomforts.
- [24] Safety follow-up: performed on days 30, 60, and 90 after the last dose. The first safety follow-up visit (day 30) will be carried out at the study center, where the evaluations specified in the protocol will be completed. The second (day 60) and the third (day 90) follow-ups will be performed via phone calls. Information on new anti-tumor treatment, survival, concomitant medications/treatments, and adverse events will be collected.
- [25] Survival follow-up: At the end of the safety follow-up period, the subjects will enter the survival follow-up period until death, lost to follow-up, withdrawal of informed consent or termination of the clinical study by the sponsor. During this period, follow-up will be conducted via phone calls or other effective methods once every 2 months to collect information on subject survival and subsequent treatments (if the subjects start a new anti-tumor treatment, the therapeutic regimen and the start and end time should be recorded).

2 FLOW DIAGRAM OF EXPERIMENT — CONTROL GROUP (DOXORUBICIN + IFOSFAMIDE OR IFOSFAMIDE MONOTHERAPY)

STUDY PROCEDURES	Screening Period		Cycle 1	Cycles 2-6	Cycles 7-16	Cycle 17 and beyond	Safety Visit ^[22]	Survival Follow- Up ^[23]

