- [19] Adverse events: Recorded from the date of signing the informed consent form to the end of the safety follow-up period or the start of a new anti-tumor treatment. See [Table 11. Principles of AE/SAE collection and follow-up](#) for details.
- [20] Concomitant medication/treatment: Recorded from 28 days before the first dose of study treatment to the end of the safety follow-up period; If a new anti-tumor treatment is started, only concomitant medications for treatment-related adverse events will be recorded thereafter. After the safety follow-up period, only concomitant medications/treatments for adverse events are required to be recorded. Subjects crossed over for SHR-1210 + apatinib treatment will be followed up according to the procedures after crossover.
- [21] Quality of life scoring: Performed within 7 days before the first dose, on day 1 of every 2 cycles in cycles 3-6, on day 1 of every 2 cycles in cycles 7-16, on day 1 of every 4 cycles from cycle 17 onwards, and at 21 days after the last dose.
- [22] Safety visit: Subjects shall go to the study center for safety visit at 21 days after the last dose in accordance with protocol requirements.
- [23] Survival follow-up: At the end of the safety follow-up period, the subjects will enter the survival follow-up period until death, lost to follow-up, withdrawal of informed consent or termination of the clinical study by the sponsor. During this period, follow-up will be conducted via phone calls or other effective methods once every 2 months to collect information on subject survival and subsequent treatments (if the subject starts a new anti-tumor treatment, the therapeutic regimen and the start and end time should be recorded).

3 SCHEDULE OF ACTIVITIES — CROSSOVER TREATMENT (SHR-1210 + APATINIB AFTER PROGRESSION FOLLOWING DOXORUBICIN + IFOSFAMIDE OR IFOSFAMIDE MONOTHERAPY)

STUDY PROCEDURES	Screening Period	Cycle 1	Cycle 2	Cycle 3 and Beyond	Safety Follow-Up ^[22]		Survival Follow-Up ^[23]
	D-7 to D-1	D1	D1	D1 (once per cycle)	30 days after the last dose	60 and 90 days after the last dose	Once every 2 months
Time Window				±3	±5	±5	±5
Signing of Informed Consent and Verification of Eligibility ^[1]	×						
ECOG PS ^[2]	×		×	×	×		
Vital Sign ^[3]	×		×	×	×		
Physical Examination ^[4]	×		×	×	×		
Virology ^[5]	×						
Hematology ^[6]	×		×	×	×		
Urinalysis ^[7]	×			×(once every 2 cycles)	×		
Fecal Occult Blood ^[8]	×		×	×	×		
Blood Biochemistry ^[9]	×		×	×	×		

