14.4.3 Secondary efficacy endpoint analysis

The analysis of secondary efficacy endpoints will be based on the FAS.

For the secondary endpoint PFS assessed by the investigator (as per RECIST v1.1), the analytical method will be the same as that of the primary endpoint mentioned above.

The secondary endpoint OS will be statistically described using the similar method for the primary endpoint. For DoR, the Kaplan-Meier method will be used to plot the survival curve and estimate the median DoR and its 95% confidence interval will be calculated (Brookmeyer-Crowley method).

For the objective response rate (ORR) and disease control rate (DCR), the rates in the two groups and their two-sided 95% CI (Clopper-Pearson method) will be estimated, and the inter-group difference of rates and its two-sided 95% CI will be calculated (CMH method).

Other endpoints will be statistically summarized in accordance with general principles.

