2.2.2 Secondary objectives

- To evaluate and compare the objective response rate (ORR) and disease control rate (DCR) of SHR-1210 combined with apatinib vs. doxorubicin combined with ifosfamide in the treatment of soft tissue sarcoma;
- To evaluate and compare the safety of SHR-1210 combined with apatinib vs. doxorubicin combined with ifosfamide in the treatment of soft tissue sarcoma;
- To evaluate and compare the quality of life scores in subjects with soft tissue sarcoma after treatment with SHR-1210 combined with apatinib vs. doxorubicin combined with ifosfamide.

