5.1.2 General rules and analysis

Baseline

Unless otherwise stated, "baseline" in this study is defined as the last non-missing measurement value obtained before the first use of study drugs.

Study days

The day of the first dose is used as the start date of the study (Day 1).

- If the evaluation date (adverse event, laboratory tests, etc.) is on or after the study medication, the study date shall be calculated as follows:

Study days = evaluation/event date – start date of study + 1.

- If the evaluation date (baseline characteristics, medical history, etc.) is before the study medication, the number of study days is a negative figure and shall be calculated as follows:

Study days = evaluation/event date – start date of study;

General analysis

Unless otherwise specified, the following descriptive statistics will be summarized by the type of variables:

- The measurement data will be summarized using mean, standard deviation, median, maximum, minimum, and quartile.
- Count data will be summarized using frequency and percentage;
- For time-to-event data, Kaplan-Meier method will be used to estimate the survival function and median time to event onset, and a survival curve will be plotted.

Number of decimal places

Unless otherwise specified, number of decimal places in the analysis report will be determined as per the following rules:

- The decimal places of the minimum and maximum will remain the same as that of raw data to be acquired; there should be one additional decimal place for the mean and median, and 2 additional decimal places for standard deviation, up to 4 decimal places.
- The percentage will be rounded to 1 decimal place. If the frequency is 0, the percentage is not displayed.
- The *P* value will retain 4 decimal places. If the *P* value is < 0.0001, it will be expressed as "< 0.0001"; if the *P* value is > 0.9999, it will be reported as "> 0.9999".
- The 95% CI, if being a decimal, will retain at least 2 decimal places, up to 4 decimal places. Details are as follows: The 95% confidence interval will have one more decimal place than that of the raw data. If the raw data have no decimal place, the 95% confidence interval will retain 2 decimal places; if the raw data have 4 or more decimal places, the 95% confidence interval will retain at most 4 decimal places.
- Time to event (in months) will be rounded to one decimal place.

Results of Laboratory Tests

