5.1.4 Missing data

In this study, the missing data of the efficacy endpoints will not be treated specially, and the missing values will not be estimated in the safety evaluation.

If the specific date of death is missing, it will be imputed based on the first day of month of death.

If the specific day of the initial diagnosis is missing, it will be imputed with the first day of the month of initial diagnosis. If the month and day of the initial diagnosis are missing and the year of the initial diagnosis is before the year of the first dose, it will be imputed with 1 Jan. If the month and day of the initial diagnosis are missing and the year of the initial diagnosis is the same as the year of the first dose, it will be imputed with 1 Jan. If the date of the initial diagnosis is completely missing, it will not be imputed.

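### Quality of life is to be compared between arms, but the plan offers only a descriptive summary, with no between-arm estimate, no use of the baseline score and no handling of scores lost after discontinuation

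*SAP*

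**What the plan says.** SAP 2.2.2 lists as a secondary objective: "To evaluate and compare the quality of life scores in subjects with soft tissue sarcoma after treatment with SHR-1210 combined with apatinib", against doxorubicin with ifosfamide. Protocol 6.1.2 has the same objective. SAP 4.1.2.4 places QLQ-C30 among the secondary efficacy endpoints, but there speaks only of evaluating the scores, not of comparing them.

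The analysis is one sentence in each document. SAP 5.4.2: "Other endpoints (best overall response, quality of life score, etc.) will be statistically summarized in accordance with general principles". Protocol 14.4.3: "Other endpoints will be statistically summarized in accordance with general principles". For numerical data the general principles are in SAP 5.1.2: "The measurement data will be summarized using mean, standard deviation, median, maximum, minimum, and quartile". On missing values, SAP 5.1.4 says: "In this study, the missing data of the efficacy endpoints will not be treated specially".

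Forms are collected at baseline and on day 1 of every second cycle from cycle 3. For control, note [21] to the flow diagram continues "on day 1 of every 2 cycles in cycles 7-16, on day 1 of every 4 cycles from cycle 17 onwards", with a last form 21 days after the last dose. For the investigational arm, note [22] has "on day 1 of every 4 cycles from cycle 17 onwards, and at 30 days after the last dose". Survival follow-up (Protocol 11.3.3) collects survival and later treatment, not quality of life.

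**The concern.** A comparison needs a contrast: a named score, a time point, a difference between arms and its uncertainty. None is given. In the same SAP section, ORR and DCR each receive a between-group difference with a 95% CI, so quality of life is the exception.

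Two further features matter for this endpoint. First, forms stop soon after treatment or scheduled assessment ends, and the design itself expects the arms to leave at different rates. Scores summarised as observed then describe different subsets of the randomised groups. Second, no scale is named. In Protocol Appendix 10, items 1-28 run from good to bad and items 29-30 from bad to good, so the plan does not say which score carries the objective.

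At stake is the trial's only patient-reported secondary endpoint. In an open-label study, the scale, visit and contrast would otherwise be chosen when results can already be seen.

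**Working it through.** **1. The plan's own figures.** No sample size, effect or power is stated for quality of life. The design figures are for PFS (SAP 2.3): medians 4.5 and 7.0 months, HR 0.64, one-sided alpha 0.025, power 90%, 1:1 allocation, 214 events, 292 subjects. Schoenfeld's formula, 4(1.960 + 1.282)² / (ln 0.64)², gives 212 events (216 with HR = 4.5/7.0). The stated 214 fits, allowing for one O'Brien-Fleming look. For dropout, 262/0.90 = 291.1, which rounds up to 292. The medians are therefore the operative design assumptions and can be used to project retention.

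**2. Expected retention.** Take exponential PFS, 21-day cycles and 292/2 = 146 subjects per arm. The progression-free share at time t is 0.5^(t/median). Day 1 of cycle c falls (c − 1) × 21/30.4375 months after C1D1.

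For C7D1, t = 126/30.4375 = 4.14 months: control 0.5^(4.14/4.5) = 0.529; investigational 0.5^(4.14/7.0) = 0.664.

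| Visit | Months | Control | Investigational | Of 146 each |
|---|---|---|---|---|
| C3D1 | 1.38 | 81% | 87% | 118 vs 127 |
| C5D1 | 2.76 | 65% | 76% | 95 vs 111 |
| C7D1 | 4.14 | 53% | 66% | 77 vs 97 |
| C9D1 | 5.52 | 43% | 58% | 62 vs 85 |
| C13D1 | 8.28 | 28% | 44% | 41 vs 64 |
| C17D1 | 11.04 | 18% | 34% | 27 vs 49 |

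The gap grows from 6 percentage points at C3D1 to about 16 around C11D1-C15D1.

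**3. What this could do to raw means.** This step rests on assumptions that are not in the documents: no true difference in quality of life, a score with SD 1, a correlation ρ between score and PFS time (normal scale), and only progression-free subjects observed. Simulated difference, investigational minus control:

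| ρ | C3D1 | C7D1 | C17D1 |
|---|---|---|---|
| 0 | 0 | 0 | 0 |
| 0.2 | −0.02 SD | −0.04 SD | −0.07 SD |
| 0.3 | −0.03 SD | −0.06 SD | −0.11 SD |
| 0.5 | −0.05 SD | −0.10 SD | −0.18 SD |

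In this model the sign is against the investigational arm, because the remaining controls are the more strongly selected group. Treatment beyond progression, toxicity dropout and unreturned forms are not modelled and could change both size and sign.

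**4. The two schedules side by side.** In the control flow diagram, study treatment is marked only through cycle 6, while note [21] schedules forms in cycles 7-16 and from cycle 17. Note [18] gives any extra chemotherapy cycles the visit content of cycles 2-6. Read together, the later columns can include controls off chemotherapy. In the investigational diagram, forms run alongside treatment. Against this, Protocol 11.2.2 lists the control forms under treatment-cycle visits and counts them in treatment cycles, and chemotherapy beyond six cycles is allowed. The schedule is ambiguous.

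**5. After progression.** Investigational subjects treated beyond progression stay on protocol visits (Protocol 8.3.3). Control subjects who cross over move to a separate schedule, and their scores are summarised separately (Protocol 14.4.9). The SAP does not say which of these scores enter the main summary.

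**The case against.** The strongest reply is that this is a phase II trial powered for PFS, with quality of life outside the alpha-controlled analysis (Protocol 14.4.8), so a descriptive secondary endpoint is acceptable. That stands as to severity. It does not remove the mismatch, because both documents say compare.

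Several stronger readings are tempting, and the documents do not support them.

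- *The comparison is biased towards control.* Bias requires the score to be related to staying under assessment. At ρ = 0 there is none, and the direction outside the simple model is unknown. Treatment beyond progression is limited to subjects without obvious decline in performance status, which complicates it further.
- *27 against 49 subjects will supply the C17D1 data.* These are progression-free counts, not form returns. They ignore discontinuation before progression, visits after it and form non-return.
- *Late visits compare controls off chemotherapy with subjects on therapy.* This is possible but not established, and control also has a post-dose form, at 21 days against 30.
- *Omitting baseline biases the result.* In a randomised comparison it costs precision. It bears on bias only once the remaining groups are selected.
- *The SAP prescribes means by visit.* It does not say how repeated scores are grouped. That is a gap, not a stated method.

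**Conclusion.** The point holds as a cheap improvement. The objective is comparative, the analysis is descriptive, and nothing in the SAP connects them. Under the design's medians and exponential PFS, the progression-free share differs by about 14 percentage points at C7D1 (0.664 − 0.529) and 15 at C17D1 (0.335 − 0.183), so raw summaries are open to selection bias. Its size is unproven: 0 to about 0.18 SD over assumed correlations of 0 to 0.5, with direction not settled. The possible mixing of on-treatment and off-chemotherapy scores at later visits is a second reason for caution, subject to the schedule's ambiguity. The PFS conclusion and the 214 and 292 figures are untouched.

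**What to change.** In SAP 5.4.2:

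- Name global health status/QoL (items 29-30) as the main scale.
- Estimate the between-arm difference in change from baseline at C3D1, C5D1 and C7D1, each with a 95% CI, from a mixed model for repeated measures with treatment, visit, treatment-by-visit, baseline score and the three randomisation factors (ECOG PS, chemotherapy-insensitive histology, prior chemotherapy).
- Report form completion by arm and visit.
- State that scores after crossover are excluded from the main comparison, and how scores after progression are used.
- Add a sensitivity analysis for data missing not at random.
- Show visits after C7D1 descriptively only, with numbers contributing.

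C7D1 is a reasonable last modelled visit because it falls one cycle after the start of the sixth recommended chemotherapy cycle, before a long chemotherapy-free interval can build up in controls. If the sponsor does not want a model, the alternative is to remove the comparison from the objective.

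The cost is SAP wording and a little analysis work. Baseline scores are already collected, and SAP section 1 describes the document as an initial version to be completed before database lock. The drawback is that the main model assumes data are missing at random given the observed scores, which is why the sensitivity analysis is needed.
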